7. STATISTICAL METHODS

Statistical Analysis Plan (SAP)

There will be a formal SAP, separate from this Trial protocol. A formal SAP will be completed prior to database lock and the analysis of any Trial endpoints data. The SAP will detail the planned statistical analyses. The subsections below summarize the planned analyses.

Primary Outcome Endpoint

The primary outcome endpoint is to determine if the use of a protocolized strategy using advanced hemodynamic monitoring with Hypotension Prediction Index (HPI) software guidance for intraoperative hemodynamic management reduces postoperative complication rate in moderate- to high-risk non-cardiac surgery. The composite includes MACE (myocardial injury, stroke, non-fatal cardiac arrest, and death), AKI, and serious infections (pneumonia, deep and organ space surgical site infections, and sepsis).

THIS DOCUMENT CONTAINS CONFIDENTIAL AND PROPRIETARY INFORMATION OF EDWARDS LIFESCIENCES, LLC. IT MAY NOT BE REPRODUCED OR DISCLOSED WITHOUT PRIOR WRITTEN PERMISSION FROM EDWARDS LIFESCIENCES, LLC.
Edwards Lifesciences, Edwards, the stylized E logo, HemoSphere, Acumen, Acumen IQ, FloTrac, and ForeSight Elite oximetry Sensor are trademarks of Edwards Lifesciences Corporation.

Sample Size Justification

The goal of this study is to assess if the use of Hypotension Prediction Index (HPI) software guidance impacts the incidence of postoperative morbidity and mortality in the adult population undergoing moderate-to-high-risk noncardiac surgery (with a pressure monitoring with an arterial line). A relative reduction in the composite outcome within the treatment arm is expected. For a group sequential analysis, following the O'Brien and Fleming methodology, a sample size was calculated for a two-sample comparison of rates (two-sided). The hypothesis are as follows:

$$H_0: p_0 - p_1 \geq 0$$

$$H_1: p_0 \neq p_1$$

Assuming at least a 25% relative change in rate for the treatment (p_1) arm, a type I error (0.05), a power of 80%, and a reference rate of 0.31 (p_0) based on a meta-analysis^{6,10,14}, a sample size of 1426 subjects are needed. An additional 60 subjects may be included as roll-ins, which results in a total enrollment potential of 1486 subjects.

Analysis Populations

Modified Intent-to-treat (mITT)

Modified Intent-to-treat (mITT) is defined as the study subjects who were exposed to the study product and will therefore be included in the effectiveness and safety analysis datasets. All randomized study subjects who have satisfied the population criteria will be classified in the designated population and will only be included in analyses for which they have available data. The mITT population will also be used to present exploratory analyses by the randomized treatment arm. The safety population is defined as all randomized subjects who were exposed to the study product; thus, the safety population will therefore be identical to the mITT population if all randomized subjects are exposed to the study product. The safety population will be used to present the safety summaries by actual treatment received.

Per Protocol Analysis

A per protocol analysis is defined as a dataset of subjects who completed enrollment as written in the protocol, (e.g., No protocol deviations occurred during the non-cardiac surgical procedures).

Analysis Methods

The following z-statistic will be used to judge if the Hypotension Prediction Index (HPI) software can reduce postoperative morbidity and mortality:

$$z = \frac{\hat{p} - \hat{p} - 0}{\sqrt{\frac{x_0 + x_1}{n_0 + n_1} \left(1 - \frac{x_0 + x_1}{n_0 + n_1}\right) \left(\frac{1}{n_0} + \frac{1}{n_1}\right)}}$$

THIS DOCUMENT CONTAINS CONFIDENTIAL AND PROPRIETARY INFORMATION OF EDWARDS LIFESCIENCES, LLC. IT MAY NOT BE REPRODUCED OR DISCLOSED WITHOUT PRIOR WRITTEN PERMISSION FROM EDWARDS LIFESCIENCES, LLC.

Edwards Lifesciences, Edwards, the stylized E logo, HemoSphere, Acumen, Acumen IQ, FloTrac, and ForeSight Elite oximetry Sensor are trademarks of Edwards Lifesciences Corporation.

Here x_0 and x_1 are the amount of events that occurred in the reference arm and test arm respectively, thus, $\hat{p} = \frac{x_0}{n_0}$, $\hat{p} = \frac{x_1}{n_1}$ are the proportion of events that occurred in the reference arm and test arm, respectively, n_0, n_1 are the number of subjects in reference arm and test arm respectively. The pooled standard error is given by $\sqrt{\frac{(x_0+x_1)}{n_0+n_1}(1 - \frac{x_0+x_1}{n_0+n_1})(\frac{1}{n_0} + \frac{1}{n_1})}$. The z-statistic will be calculated using data from the complete case population and it will be compared to the critical z-value ($z(\alpha', n_0 + n_1 - 2)$) to judge if the null hypothesis can be rejected. Here α' is the adjusted type I error rate (adjusted for interim analysis). Moreover, the degree of freedom is given by, $n_0 + n_1 - 2$. The 95% CI is given by $\hat{p} - \hat{p} \pm z_{\alpha} \sqrt{\frac{(x_0+x_1)}{n_0+n_1}(1 - \frac{x_0+x_1}{n_0+n_1})(\frac{1}{n_0} + \frac{1}{n_1})}$. The other analysis methods are detailed in the statistical analysis plan.

Additional Evaluations

The continuous variables will be evaluated using the parametric two sample t-test (or the Welch t-test if unequal variance or the Wilcoxon-Mann Whitney test if non-normally distributed) and categorical/binary variables will be evaluated using a chi-squared test (Fisher's exact if low counts). Logistic regression will be used to evaluate incidence of AKI with other variables being used as co-variates. Time-to-event variables will be evaluated by survival analysis models (Kaplan-Meier or Cox Proportional Hazards). Summary statistics and statistical comparison will be presented in tables with point estimates (odds ratios or log odds), standardized errors, and 95% CI. There will be no multiplicity adjustment for performing multiple hypothesis tests of exploratory outcomes, unless specified otherwise.

Sensitivity analysis including the review of any influence of surgical position, type of anesthesia, tidal volume etc., on the primary outcome measure, are specified in the SAP.

The following data will also be explored:

1. Time-to-Adverse Event (Complications) Analysis
 - a. Non-Parametric Survival Analysis (KM approach)
 - b. Cox Proportional Hazard Model
 - c. Mixed effect Cox Proportional Hazard Model
 - d. Stratification analysis through applying study sites, gender, race as the stratification factor
 - e. Fixed/Mixed effective Poisson regression model applying the count of events as the response
 - f. Mixed effective survival model to assess the multiple event cases within patient
2. Hypotension management analysis
 - a. Time from alert event to intervention
 - b. % alerts with no intervention
 - c. Reasons for nonintervention
 - d. Amount of hypotension removing nonintervention segments
 - e. Agreement analysis; clinical decision vs. treatment algorithm
 - f. Overall treatment protocol compliance
3. Area under the curve AUC MAP under the threshold of 55,65,75 mmHg

THIS DOCUMENT CONTAINS CONFIDENTIAL AND PROPRIETARY INFORMATION OF EDWARDS LIFESCIENCES, LLC. IT MAY NOT BE REPRODUCED OR DISCLOSED WITHOUT PRIOR WRITTEN PERMISSION FROM EDWARDS LIFESCIENCES, LLC.

Edwards Lifesciences, Edwards, the stylized E logo, HemoSphere, Acumen, Acumen IQ, FloTrac, and ForeSight Elite oximetry Sensor are trademarks of Edwards Lifesciences Corporation.

4. Time Weighted Average (TWA) of intraoperative hypotension (mmHg)
5. Time in target SVV <13% (for valid SVV readings = no arrhythmia)
6. Time in target CI >2.5 L/min/m¹⁵
7. Postoperative morbidity survey (POMS) on postoperative day 3
8. Transfusion requirement (mL packed red blood cells)
9. Amounts of intraoperative crystalloid and colloid and vasoactive drugs; mL
10. Amount of vasoactive drugs; mg (e.g.: phenylephrine, ephedrine, norepinephrine, epinephrine, dobutamine)
11. Amount of intraoperative intravenous analgesics and sedatives
12. Brain oxygen saturation – StO₂ using ForeSight Elite tissue oximetry system, time in target
13. Verification of the incidence of the listed postoperative complications may be performed at each site by reviewing historic data up to 6 months prior to study initiation
14. Cost of care
15. Hospital length of stay
16. Hospital readmission within 30 days

Planned Interim Analyses

Assuming a power of 80% and a relative reduction of at least 25% in the composite score (reference proportion=0.31) with three total looks (two interim analysis, one final), the critical values for each time point were chosen to preserve an overall type-1 error rate of 0.05. The O'Brien and Fleming methodology was used to determine the boundary rule for deciding when to stop the trial prematurely. Futility was included. A relative reduction in the composite outcome within the treatment arm is expected. The alpha at each interim and the maximum number of observations are chosen so that the overall significance level is the probability of detecting the treatment difference under the null hypothesis. The table below shows the critical values:

Analysis	Information Rate	Effectiveness Boundary z-value (Upper, Lower)	Futility Boundary z-value (Upper, Lower)
First Interim Analysis	50%	(2.96259, -2.96259)	(0.40273, -0.40273)
Second Interim	75%	(2.35898, -2.35898)	(1.12741, -1.12741)
Final Analysis	100%	(2.01404, -2.01404)	(2.01404, -2.01404)

THIS DOCUMENT CONTAINS CONFIDENTIAL AND PROPRIETARY INFORMATION OF EDWARDS LIFESCIENCES, LLC. IT MAY NOT BE REPRODUCED OR DISCLOSED WITHOUT PRIOR WRITTEN PERMISSION FROM EDWARDS LIFESCIENCES, LLC.

Edwards Lifesciences, Edwards, the stylized E logo, HemoSphere, Acumen, Acumen IQ, FloTrac, and ForeSight Elite oximetry Sensor are trademarks of Edwards Lifesciences Corporation.

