Trial Objective:	To determine if the use of a protocolized strategy using advanced hemodynamic monitoring with Hypotension Prediction Index (HPI) software guidance for intraoperative hemodynamic management reduces postoperative complication rate in moderate- to high-risk non-cardiac surgery.
Primary Effectiveness Endpoint:	The primary hypothesis is that the administration of advanced hemodynamic monitoring utilizing the Hypotension Prediction Index (HPI) with a protocolized strategy during moderate-to-high-risk noncardiac surgery reduces composite of severe postoperative complications at 30 days. The composite includes: Major adverse cardiac events MACE (myocardial injury, stroke, non-fatal cardiac arrest, and death), acute kidney injury (AKI), and serious infection. Specifically, we seek to evaluate if the treatment protocol utilizing the technology from Edwards Lifesciences will result in a relative change of at least 25% in the composite complication score when compared to the control arm that will receive an arterial line with only blood pressure monitoring, as per the standard of care.
Trial Devices:	HemoSphere Advanced Monitor, Acumen™ HPI Feature Software, Acumen IQ sensor, FloTrac sensor, and ForeSight Elite Oximetry sensor.
Overall Design:	A multicenter, randomized comparison of intraoperative hemodynamic management with or without a protocolized strategy utilizing Hypotension Prediction Index (HPI) software guidance during moderate-to-high-risk noncardiac surgery.
Trial Population:	Up to 1486 adults undergoing moderate-to-high-risk noncardiac surgery who will be receiving pressure monitoring with an arterial line.
Number of Sites:	Up to Twenty (20) U.S. Sites
Trial Duration:	Total of 24 to 36 months
Participation Duration:	Screening/Baseline; Procedure; Post-Op Days 1-3; ICU; hospital discharge; 30-day Telephone Follow-Up Visit
Inclusion/Exclusion Criteria	Inclusion Criteria: 
1. Signed informed consent;2. Age \geq 18 years;

THIS DOCUMENT CONTAINS CONFIDENTIAL AND PROPRIETARY INFORMATION OF EDWARDS LIFESCIENCES, LLC. IT MAY NOT BE REPRODUCED OR DISCLOSED WITHOUT PRIOR WRITTEN PERMISSION FROM EDWARDS LIFESCIENCES, LLC.

Edwards Lifesciences, Edwards, the stylized E logo, HemoSphere, Acumen, Acumen IQ, FloTrac, and ForeSight Elite oximetry Sensor are trademarks of Edwards Lifesciences Corporation.

3. ASA Physical Status \geq 2;

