 Edwards	Revision Date: May 11, 2022		Rev	A	For Use Only by Affiliates of Edwards Lifesciences	Page 6 of 19
	Title	Statistical Analysis Plan for HP/ SMART-BP Trial				

estimation, and is supported by the integrated evidence from physician clinical experience, scientific publications, and previous clinical trial results.

The hypothesis setting for this study used in sample size estimation is:

$H_0: P_1 \geq P_0$

$H_1: P_1 < P_0$

where p_1 and p_0 are the proportions of composite endpoint in treatment arm and control arm, respectively.

Moreover, two interim analyses will be designed at 50% and 75% subject enrollment with 30-day follow-up data, to assess the composite endpoint (pooled event rate) between treatment and control arms. To determine when the trial can be stopped prematurely for effectiveness, the O'Brien-Fleming methodology¹⁶ was used to determine the stopping boundary (alpha spending function). The O'Brien-Fleming methodology preserves the overall type I error across all interim analyses¹⁶. The overall type I error used for this one tail hypothesis test study is 0.025. If the Z-statistics is close to boundary value but could not reject null hypothesis, possibly the study sample size will be reassessed for the purpose to achieve study objective.

With these trial parameter and hypothesis settings, and two designed interim analyses plus a final analysis, 1486 subjects (including 15% attrition, including a maximum of 60 roll-ins) are needed for this clinical trial. The sample size is estimated with PASS2021. The critical Z value and the corresponding p value for effectiveness boundary are displayed in the following table for interim analysis and final analysis. By the study objective and experiment design, in effectiveness analysis if the Z value calculated by the data available at each study stage (interim analysis and final analysis) is less or equal the critical Z value listed in effectiveness boundary column, the null hypothesis will be rejected, and the study stops for the study objective is achieved. To simplify the interim analysis decision making procedure, the lower limit of the reference arm accumulated subjects with complication, and the upper limit of treatment arm accumulated subjects with complication are designed by the study design parameters, the study arm accumulated sample size at each analysis stage, and effectiveness boundary (critical Z value) estimated by O'Brien-Fleming methodology.

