By the study designed parameter table in section 2.3 and the Z statistic calculated at each study stage with the trial data collected at present stage in addition to data collected in previous stage or stages, following judgement will be conducted for interim analysis and final analysis. For first and second interim analyses, if the calculated Z value is equal to or less than the critical Z value in the effectiveness boundary column, the null hypothesis will be rejected, and the study will stop for achieving the study objective; if the calculated Z statistic is greater than critical Z value for effectiveness but it is close to the critical value but could not reject null hypothesis, the study continues to next step, and the study sample seize will be reassessed by the principles of adapted group sequential study design. If it is necessary, more study subject will be enrolled for the purpose to achieve the study objectives. For final analysis, if the calculated Z statistic is equal to or less than the critical Z value listed in effectiveness boundary column, the null hypothesis will be rejected, and the alternative hypothesis will accept, the study objective is achieved, otherwise, the null hypothesis will accept, the study objective will be not achieved.

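### The protocol prints the hoped-for benefit as its null hypothesis, the SAP tests a different hypothesis with its Z pointing the wrong way, and one synopsis sentence poses a 25% question that no test answers

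*Combined protocol and SAP*

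**What the plan says.** **Protocol 7, Sample Size Justification.** The text states that "a sample size was calculated for a two-sample comparison of rates (two-sided). The hypothesis are as follows", and prints H0: p0 − p1 ≥ 0 and H1: p0 ≠ p1. The subscripts are defined nearby: "Assuming at least a 25% relative change in rate for the treatment (p_1) arm, a type I error (0.05") makes p1 the treatment rate, and "a reference rate of 0.31 (p_0") makes p0 the control rate. Under Analysis Methods, "x_0 and x_1 are the amount of events that occurred in the reference arm and test arm respectively" confirms this. The Planned Interim Analyses table gives upper and lower efficacy bounds for an overall error of 0.05.

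**SAP 2.3.** The hypotheses are H0: P1 ≥ P0 and H1: P1 < P0. "The overall type I error used for this one tail hypothesis test study is 0.025". The efficacy bounds are −2.96259, −2.35898 and −2.01404. A second table gives final-look limits of 222 control and 186 treatment events and a required reduction of 0.16.

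**SAP 8.1.** Z is defined with p̂0 − p̂1 in the numerator. The null is rejected if Z is at or below the negative critical value, in which case "the alternative hypothesis will accept, the study objective is achieved".

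**SAP 10.** No changes from the protocol-specified analyses are declared.

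**Synopsis, Primary Effectiveness Endpoint.** After a hypothesis that the composite is reduced, a further sentence says the sponsor seeks to evaluate if the treatment protocol "will result in a relative change of at least 25% in the composite complication score when compared to the control arm".

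**The concern.** A primary hypothesis should say, before any data are seen, which results count for the treatment. As printed, the protocol's does not. Its null is true whenever treatment is equal to or better than control, so rejecting it would be evidence of harm, and any true benefit satisfies both H0 and H1. The SAP has the right pair, but its Z and its bounds have opposite signs, so the printed decision rule also points at harm. The two documents differ in direction and in sidedness, and the section meant to record differences records none.

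The 25% sentence is a separate and smaller matter. It puts a question to the trial that no hypothesis, bound or success rule addresses. A reader of a positive result could take it as evidence for a reduction of at least 25%.

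**Working it through.** **1. Which region is the protocol's null?** With p0 = control and p1 = treatment, p0 − p1 ≥ 0 is the same as p1 ≤ p0. The design alternative has p0 = 0.31 and p1 = 0.31 × 0.75 = 0.2325, so p0 − p1 = 0.0775 ≥ 0. The effect the trial is sized for lies inside the printed null, and also inside H1. SAP 2.3 puts the same point only in H1.

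**2. Does sidedness change the efficacy test?** Overall one-sided error is 1 − P(Z1 < 2.96259, Z2 < 2.35898, Z3 < 2.01404) for a trivariate normal at information 0.5, 0.75 and 1. This gives 0.0250; the symmetric two-sided version gives 0.0500. The nominal one-sided p-values are 0.00153, 0.00916 and 0.02200, as the SAP prints. The fixed-design sample size for 0.31 against 0.2325 at 80% power is 1032 under either convention. Sidedness therefore changes no efficacy bound and no N. It decides only whether harm can be formally declared.

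**3. The SAP's 0.16.** The pivotal total is 1486 − 60 = 1426, or 713 per arm at 1:1. The table fits that size: 0.31 × 713 = 221.03, and the next whole number is 222.
- From the counts: 1 − 186/222 = 0.162.
- From the boundary, solving (0.31 − p1)/√[(0.31 × 0.69 + p1(1 − p1))/713] = 2.01404 gives p1 = 0.262, a reduction of 15.5%.
- With 606 per arm (713 × 0.85, after the SAP's 15% attrition) it is 16.8%.

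The printed figure is reproduced.

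**4. The SAP 8.1 rule at its own limits** (713 per arm). p̂0 = 222/713 = 0.3114 and p̂1 = 186/713 = 0.2609. The standard error is √[(0.3114 × 0.6886 + 0.2609 × 0.7391)/713] = 0.0239. Z = (0.3114 − 0.2609)/0.0239 = +2.11. The rule requires Z ≤ −2.01404, so read literally this result, which the table treats as success, does not reject. Exchange the arms (186 control, 222 treatment) and Z = −2.11: the literal rule rejects and declares the objective achieved.

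**5. What that result says about 25%.** The relative risk is 186/222 = 0.838. The standard error of its log is √(1/186 − 1/713 + 1/222 − 1/713) = 0.0841. The 95% CI is exp(−0.177 ± 1.96 × 0.0841), or 0.71 to 0.99, a reduction of about 1% to 29%. The interval excludes no effect but not reductions below 25%. For the lower confidence limit to reach 25% (control 0.31, 713 per arm, z = 2.014), the observed reduction would have to be about 38%.

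**6. The role of 25% elsewhere.** The protocol Background calls it a target, Trial Endpoints an expectation, Sample Size Justification an assumption, and SAP 2.3 an expected effect used for sizing. Only the synopsis sentence makes it the question.

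**The case against.** The best defence is that the protocol null is a slip, possibly of reading. The formulas were recovered by program and are damaged nearby: the protocol's z numerator has lost its subscripts. An original equality sign would fit both the trailing zero in that numerator and the two-sided alternative, and this text cannot exclude it. The intended direction is plain throughout: the objectives speak of reducing complications, a reduction is expected, the SAP has the correct null, and the event-limit table rewards fewer treatment events. All of that stands and is why the severity is moderate. It does not remove the point. Even with an equality, the protocol would be two-sided and the SAP one-sided with no change declared, and the sign conflict between the SAP's Z and its bounds would remain.

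Four stronger readings are tempting, and the documents do not support them.
- *The 25% aim is declared met at an observed 16%.* SAP 8.1 declares the study objective achieved, and that objective (SAP 2.1, 3.1, 8.1) is a reduction with no threshold.
- *A significance threshold below the design effect is a flaw.* It is normal in any superiority trial with power above 50%.
- *The trial as planned cannot support its claim.* Run on the SAP hypotheses in the evident direction, it can show a reduction, which is the protocol's primary objective.
- *Success at smaller true effects shows an error.* With 713 per arm and no futility stopping, success is about 25%, 48% and 90% at true reductions of 10%, 15% and 25%; with 606 per arm and the protocol's futility bounds it is about 20%, 41% and 84%. That is ordinary power.

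**Conclusion.** The primary hypothesis is wrong as written in the protocol, contradicted by the SAP, and not rescued by the SAP's decision rule, whose Z and bounds have opposite signs. The severity is moderate: the intended test can be inferred, and overall error, efficacy bounds and N are the same after correction. The remaining substantive difference is whether harm can be formally declared.

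The 25% point is narrower: one synopsis sentence poses a question that the analysis does not address, and a result at the SAP's final limits would not answer it. The interval of about 1% to 29% assumes 713 analysed per arm and exactly 222 and 186 events. The conclusion on direction rests on the hypotheses and the SAP formula as they read in this text.

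**What to change.** - **Protocol 7:** state H0: p1 ≥ p0 against H1: p1 < p0 at one-sided 0.025, as in SAP 2.3, and bring the wording on sidedness and the interim table into line.
- **SAP 8.1:** define Z with p̂1 − p̂0, so that benefit is negative and matches the negative bounds in SAP 2.3 and 8.1. Use the same order in the protocol's Analysis Methods. Aligning the protocol to SAP 2.3 alone would leave the decision rule pointing at harm.
- **SAP 10:** list the change from two-sided 0.05 to one-sided 0.025.
- **Synopsis:** say that the trial tests whether the strategy reduces the composite and is sized for a 25% relative reduction.
- **Reporting:** give the relative risk with its confidence interval, and claim a reduction of at least 25% only if the interval supports it.

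The cost is wording. No patients are added, and the efficacy bounds and N stay as they are. The stated claim becomes slightly less favourable, and a one-sided design has no formal test for harm.

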2.3 Sample Size Consideration

Meta-analysis approach is used to optimally integrate the valid information collected from literature. Here, the statistics (pooled effect sizes (ES)) from the meta-analysis construct the composite endpoint for the reference (control) group. Composite endpoint is comprised of the following components: (1) MACE (myocardial injury¹²¹, stroke, non-fatal cardiac arrest, and death), (2) AKI (KDIGO stage 2-3), and (3) infection (pneumonia, deep surgical site, and organ space surgical site).

The event rate (pooled effect size) of the control arm to be given is 0.31. This event rate was calculated using the weighted average methodology where the final event rate is based on the sample sizes as the weight from following manuscripts, Futier et al.¹⁷¹, Pearse et al.¹³¹, and Maheshwari et al.¹⁹¹. The algorithm formula is: $ES = \frac{\sum w_i \cdot e_i}{\sum w_i}$. Moreover, for manuscripts in which individuals who experienced MINS, stroke or death simultaneously were observed, an adjustment was conducted so that there is no overcounting within the meta-analysis. The event rate for the components MACE, AKI, and infection is as 0.06788, 0.10217, and 0.17182 respectively. Please see algorithm listed below the table using in the meta-analysis and final composite endpoint computation.

Sample Size	• • • •			AKI(%)	Infection (%)		
	■	■	■		Renal	Deep Surgical Site	Organ Space Surgical Site
n=145	■	■	■	6.5	17.9	0	24.8
n=364	■	■	■	3.0	4.7	01	9.9
n=108	■	■	■	(J:1)3	18.5	31.5 ³	0
Composite	6.288			10.217	17.182		

$$\text{Compilation Composite} = 1 - (1 - 0.06788) * (1 - 0.10217) * (1 - 0.17182) = 0.30690$$

Although there are other derivations of the meta-analysis including Fleiss's inverse variance methodology¹⁵¹ (Please see appendix section 12.1, 12.2, and 12.3), this conservative control arm final composite endpoint estimate (0.31) is selected to estimate sample size for this clinical trial, due to this being more reflective of what is observed in clinical practice. A 25% reduction of the composite endpoint by the treatment arm is expected for this trial, which is used in sample size

¹ Did not report deep alone, this statistic was merged with other infection types.

² MINS rate was adjusted for overcounting, original rate for MINS 7/108 (6.7%) 5/108 (4.6%)

³ Deep Surgical Site Infection rate was adjusted for overcounting, original rate 35/108 (32.4%) 34/108 (31.5%)

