Analysis	Information Rate	Alpha Spending Function	Effectiveness Boundary Critical Z value	P-Value
First Interim	50%	O'Brien-Fleming	-2.96259	0.00153
Second Interim	75%	O'Brien-Fleming	-2.35898	0.00916
Final Analysis	100%	O'Brien-Fleming	-2.01404	0.02200

Analysis	Information Rate	Proportion of Control Subject with Complications	Required Reduction Rate	Control Arm Limit (2::)	Treatment Arm Limit (<)	Subject Ratio(<)*
First Interim	50%	0.31	0.33	111	74	0.67
Second Interim	75%	0.31	0.21	167	131	0.78
Final Analysis	100%	0.31	0.16	222	186	0.84

Note: * Subject Ratio = Treatment Arm Limit / Control Arm Limit.

 Edwards	Revision Date: May 11, 2022		Rev	A	For Use Only by Affiliates of Edwards Lifesciences	Page 7 of 19
	Title	Statistical Analysis Plan for HPI SMART-BP Trial				

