6.2 Handling of Missing Data

Missing data are defined as those instances in which data collection was attempted yet failed for some reason (i.e., due to technological, procedural, and/or subject dropout). Demographic and baseline characteristics are collected from the study subjects as part of screening. Subjects who do not meet all criteria will not be enrolled into this study. Subjects who are not randomized are considered as screening failures. Data for screening failure subject will not be captured.

If missing data are not related to the subject's eligibility criteria, missing data will be presented as not reported in the demographic and baseline characteristics summary statistics table. These subjects will be included in all analysis. However, if the missing data are related to the subject's eligibility, this will be considered a protocol deviation, and in this case, the study data from this subject will be reviewed internally, to determine if the subject should be excluded from analysis set.

The hemodynamic measurements are downloaded from the monitor platform. Theoretically, there should be no missing data. If there are missing values in the hemodynamic parameters download from monitor platform caused by any reason, the last value will be carried forward.

For binary or categorical data that are missing as defined above, single imputation will be used. For continuous data that are missing as defined above, statistical imputation using the multiple imputation (MI) method.

By the data from similar clinical trial sponsored by Edwards LifeSciences, missing value of the primary effectiveness endpoint is really rare (less than 1%). In case, more than 5% study subjects with missing primary effectiveness endpoint, imputation techniques with different missing mechanisms (multiple imputation approach with assumption missing at complete random, missing at random, or tipping point analysis approach for missing not at random), mentioned in National Research Council publication ^[18], will apply to impute the missed values. Sensitivity analysis for primary

 Edwards	Revision Date: May 11, 2022		Rev	A	For Use Only by Affiliates of Edwards Lifesciences	Page 11 of 19
	Title	Statistical Analysis Plan for HPI SMART-BP Trial				

effectiveness endpoint will conduct on pivotal mITT data with imputed values to check the robustness of statistical analysis outcome.

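### 1,426 pivotal subjects give about 90% power on the plan's inputs (about 85% after 15% loss), not 80%; the two documents treat attrition in the same 1,486 differently, and SAP 2.3 misdescribes what the 0.31 control rate covers

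*Combined protocol and SAP*

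**What the plan says.** Protocol section 7 (Sample Size Justification) assumes a control rate of 0.31, a 25% relative reduction, type I error 0.05 and 80% power, and concludes that "a sample size of 1426 subjects are needed". It continues: "An additional 60 subjects may be included as roll-ins, which results in a total enrollment potential of 1486 subjects". It mentions no attrition. Under Planned Interim Analyses the protocol prints efficacy and futility bounds and notes "Futility was included", without saying whether futility is binding.

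SAP 2.3 reaches the same total by another account: "1486 subjects (including 15% attrition, including a maximum of 60 roll-ins) are needed for this clinical trial". It does not say what the 15% covers. SAP 6.2 expects fewer than 1% of primary endpoints to be missing, based on a similar trial of the sponsor. SAP 2.3 also gives control-arm count limits of 111, 167 and 222 for the three looks at a rate of 0.31.

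On the control rate, SAP 2.3 includes non-fatal cardiac arrest in MACE and describes the infection component as "infection (pneumonia, deep surgical site, and organ space surgical site"). It then states: "The event rate for the components MACE, AKI, and infection is as 0.06788, 0.10217, and 0.17182 respectively". The primary endpoint in SAP 3.1 also includes sepsis.

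**The concern.** A two-arm comparison of 0.31 with 0.2325 at 80% power needs roughly a thousand subjects, so 1,426 looks too large for the power claimed. Attrition would be the natural explanation, but only the SAP mentions it, and the protocol reaches the same 1,486 without it.

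At stake is whether a reader can tell what power the trial has and how much loss it tolerates. The SAP also allows the sample size to be reassessed at an interim look, and that needs one agreed starting size and power. Separately, if 0.31 does not cover the components listed for it, an observed rate for the full endpoint cannot be compared with it like for like.

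**Working it through.** **Inputs.** p0 = 0.31 and p1 = 0.75 × 0.31 = 0.2325, so the difference is 0.0775 (protocol 7, SAP 2.3). Allocation is 1:1. Looks are at 50%, 75% and 100% of information, with efficacy bounds 2.96259, 2.35898 and 2.01404 (both documents). Futility bounds are 0.40273 and 1.12741 (protocol only).

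**1. Boundaries.** Numerical integration over the three looks gives a one-sided type I error of 0.0250. This matches SAP 2.3 and corresponds to the protocol's two-sided 0.05.

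**2. Size for 80% power.** n per arm = d² × V / 0.0775², where d is the drift at full information that gives 80% power.
- V unpooled (the form in SAP 8.1) = 0.31 × 0.69 + 0.2325 × 0.7675 = 0.39234.
- V pooled (the form in the protocol) = 2 × 0.27125 × 0.72875 = 0.39535.
- Efficacy bounds only: d = 2.829, so n = 523 (unpooled) to 527 (pooled) per arm, or 1,046–1,054 in total.
- Futility binding: d = 2.896, so n = 548 to 552 per arm, or 1,096–1,104 in total.

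The plan's 1,426 is not reproduced. Stacking a continuity correction, futility and 15% attrition (dividing by 0.85) reaches only about 1,360.

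**3. Power at the planned size.**

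| Evaluable | Per arm | Efficacy bounds only | Futility binding |
|---|---|---|---|
| 1,426 (no loss) | 713 | 90.4–90.6% | 89.0–89.2% |
| 1,412 (1% missing: 1,426 × 0.99) | 706 | 90.1–90.3% | 88.7–88.9% |
| 1,212 (15% lost: 1,426 × 0.85) | 606 | 85.2–85.5% | 83.6–83.8% |

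If the 15% was instead added on top, 1,426 / 1.15 = 1,240 evaluable, with about 86% power (84–85% with futility). Power stays at or above 80% until about 26% are lost (1 − 1,054/1,426 = 26.1%), or about 23% with binding futility (1 − 1,104/1,426 = 22.6%).

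**4. Count limits in SAP 2.3.** The control limit is 0.31 × n per arm × information fraction.
- 714 to 716 per arm (rounded up) or 717 (nearest) gives 111/167/222, as printed.
- 713 gives 110.5/165.8/221.0.
- 606 gives 93.9/140.9/187.9.

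The table therefore assumes that essentially all 1,426 are analysed, with no attrition removed.

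**5. What 0.31 covers.** The three source studies have 145, 364 and 108 control subjects, 617 in total.
- Infection, deep plus organ-space only: (145 × 0.248 + 364 × 0.099 + 108 × 0.315)/617 = 0.17182, exactly the rate used.
- Pneumonia would add (145 × 0.110 + 364 × 0.107)/617 = 0.08898, giving 0.2608. Sepsis would add 145 × 0.262/617 = 0.06157, giving 0.3224.
- MACE: (145 × 0.062 + 364 × 0.052 + 108 × 0.1293)/617 = 0.06788. SAP 12.1.1 names the three terms in each bracket as MINS, stroke and death. Cardiac arrest is not among them.
- Composite: 1 − (1 − 0.06788)(1 − 0.10217)(1 − 0.17182) = 0.307, which agrees with the plan's 0.30690.

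**6. SAP 12.1.** The formulas as they read give infection rates of 0.2608 and 0.3224, against printed values of 0.32392 and 0.38549. The difference in both is 364 × 0.107/617 = 0.06312. The printed composites are sums (0.06788 + 0.10217 + 0.32392 = 0.49397; with 0.38549, 0.55554), although a product is displayed.

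**The case against.** The protocol says that its statistical subsections summarise and that the SAP gives the detail. Both documents arrive at 1,486, so the protocol's silence on attrition can be read as an omission. That softens the conflict over attrition but does not rescue the 80%, because 1,212 evaluable subjects still give about 85%.

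The plan also calls 0.31 conservative and expects a rate of at least 31%. This stands as to direction: adding the omitted infection components would give about 0.381 (with pneumonia) or 0.433 (with sepsis as well), and at the same 25% relative reduction power at 713 per arm would be about 97% or 99%. It does not make the component list correct.

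Several stronger readings are tempting and are not supported:
- A reader might infer that the 15% is an error to be deleted, since SAP 6.2 expects under 1% missing. The 15% is undefined and could cover withdrawals, aborted procedures or randomised subjects who fall outside the mITT population. The documents do not show that it means missing endpoints.
- A reader might infer that 15% was applied twice, because 1,054 / 0.85 = 1,240 and 1,240 × 1.15 = 1,426. That needs pooled variance, no futility and two different inflation conventions. The same steps give 1,415 from 1,046 and 1,483–1,494 with futility. The PASS settings are not shown.
- A reader might take 0.49 or 0.55 from SAP 12.1 as the right control rate. Those figures do not follow from the formulas beside them. The equations also read badly in the available text, and one lost 0.107 term would explain the infection rates, so they need checking before any correction.

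**Conclusion.** The point holds as a correction of stated figures. On the plan's own inputs, 1,426 is about 370 to 380 more than 80% power requires (1,426 − 1,054 = 372; 1,426 − 1,046 = 380), or 322 to 330 more if futility binds (1,426 − 1,104; 1,426 − 1,096). Stated size and stated power do not match with or without the SAP's 15%. The two documents account differently for the same 1,486, and the SAP's count table follows the no-loss account. The component list for 0.31 in SAP 2.3 is wrong for pneumonia and non-fatal cardiac arrest, and sepsis is absent from the rate although it is in the endpoint.

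The trial is not shown to be underpowered or invalid: the discrepancies run towards more power than stated. The figures assume that 0.31 and the 25% reduction are true and that the looks fall as planned. The SAP 12.1 slips do not affect sample size or power.

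**What to change.** Keep enrolment at 1,426 plus 60 roll-ins. Check the PASS inputs, then state in identical words in both documents one attrition assumption, what it covers, the resulting power and whether futility is binding. Either of these would be consistent:
- 1,426 randomised, about 1,412 evaluable at 1% missing, about 90% power (about 89% if futility is binding); or
- 1,426 randomised, 1,212 evaluable after 15% attrition, about 85% power (about 84% if futility is binding).

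Recompute the control and treatment columns of the SAP 2.3 count table at the chosen number per arm. At 706 the expected control counts are 109.4/164.2/218.9 (0.31 × 706 × 0.5, 0.75 and 1); at 606 they are 93.9/140.9/187.9.

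In SAP 2.3, say that 0.31 covers MINS, stroke, death, AKI and deep or organ-space infection only, without pneumonia, sepsis or non-fatal cardiac arrest.

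As a minor erratum, check the SAP 12.1 infection rates against their formulas and recompute the composites as the product shown.

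The cost is one paragraph in each document, one component list, one table and some appendix arithmetic. No extra patients are needed, and the boundaries, test and endpoint are unchanged.
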